## 6.5. Concomitant Therapy

Medications taken within 28 days before the first dose of trial medication will be documented as a prior medication. Medications taken after the first dose of trial medication will be documented as concomitant medications.

Concomitant Treatment is defined as ongoing or initiated at any time on or after baseline (Day 1) of the study through the final study visit. Concomitant treatments include any substance ingested, injected, absorbed, inhaled, or otherwise enters the body for a therapeutic purpose regardless of number of doses taken. This includes prescription and over-the-counter medicines, vitamins, and herbal remedies.

Participants may use supplements and medications during the course of the study with the exception of those listed in package insert. Medication considered to be standard of care are permitted but should be recorded on the CRF. If a participant is offered, in accordance with the prevailing local guidelines, a COVID-19 vaccine, it should be permitted. This would be recorded as a concomitant medication and standard AE collection and reporting processes would be followed.

### Prohibited Therapies:

1. Use of non-steroidal anti-inflammatory drugs (NSAIDs) other than those noted below is prohibited. Some NSAIDs, like diflunisal, can bind to the thyroxine binding sites on transthyretin. Chronic use (greater than 4 times/month) of NSAIDs before the study is prohibited except the following permitted NSAIDs: acetylsalicylic acid, etodolac, ibuprofen, indomethacin, ketoprofen, nabumetone, naproxen, nimesulide, piroxicam, and sulindac. Topical ophthalmic NSAIDs administered while the patient's nasal punctum is occluded are also permitted.
2. Use of any investigational drug or vaccine during the study is prohibited.
3. Additionally, the use of diflunisal, taurooursodeoxycholate and doxycycline or any other TTR stabilizing agent or experimental interventions for transthyretin amyloid cardiomyopathy within 30 days prior to the study entry and/or during study participation is not permitted.
4. Digitalis and calcium channel blockers (eg, verapamil, diltiazem) are prohibited concomitant medications because they bind to amyloid fibrils and may lead to increased toxicity.
5. Use of any dosage form of tafamidis before the study is prohibited.

Contraindicated therapies must be in accordance with investigational drug package insert.

Hormonal contraceptives that meet the requirements of this study are allowed to be used in participants who are women of childbearing potential (WOCBP) (see [Appendix 4](#)).

Use of traditional Chinese medicine should obtain the permission of investigator.

#### **6.5.1. Rescue Medicine**

There is no rescue therapy to reverse the adverse events (AEs) observed with tafamidis; standard medical supportive care must be provided to manage the AEs.

#### **6.6. Dose Modification**

Not applicable.

#### **6.7. Intervention After the End of the Study**

No intervention will be provided to study participants at the end of the study. Participants should refer to routine clinical care procedure with consulting from clinical physicians after end of the study.

### **7. DISCONTINUATION OF STUDY INTERVENTION AND PARTICIPANT DISCONTINUATION/WITHDRAWAL**

#### **7.1. Discontinuation of Study Intervention**

Participants with one or more of the following criteria in the study duration will discontinue the investigational drug:

Experience adverse events that may be associated with the tolerability of treatment with tafamidis, other safety criteria(eg, AE, PK criteria), disease state criteria (eg, progressive disease), etc. The site has the option to discontinue dosing for this participant and to terminate the participant's study participation.

Note that discontinuation of study intervention does not represent withdrawal from the study unless the patient requests withdrawal from the study. If study intervention is definitively discontinued, the participant will remain in the study to be evaluated for the End of Treatment visit (within 2 weeks after the End of Treatment date). See the [SoA](#) for data to be collected at the time of discontinuation of study intervention and follow-up for any further evaluations that need to be completed. In the event of early Study Intervention Discontinuation, the site staff will follow-up on the participant's vital status at Month 12 from baseline (or at Early Study Discontinuation visit for a participant who withdraws consent for any further contact).

In the event of discontinuation of study intervention, it must be documented on the appropriate CRF/in the medical records whether the participant is discontinuing further receipt of study intervention or also from study procedures, posttreatment study follow-up, and/or future collection of additional information.

## ECG Changes

A participant who meets either bulleted criterion based on electrocardiogram (ECG) readings will be withdrawn from the study.

QTcF >500 msec.

Change from baseline: QTc >60 msec.

If a clinically significant finding is identified (including, but not limited to, changes from baseline in QTcF after enrollment), the investigator or qualified designee will determine if the participant can continue in the study and if any change in participant management is needed. This review of the ECG printed at the time of collection must be documented. Any new clinically relevant finding should be reported as an AE.

See the [SoA](#) for data to be collected at the time of intervention discontinuation and follow-up and for any further evaluations that need to be completed.

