#### **7.2.1. Withdrawal of Consent**

Participants who request to discontinue receipt of study treatment will remain in the study and must continue to be followed for protocol-specified follow-up procedures. The only exception to this is when a participant specifically withdraws consent for any further contact with him or her or persons previously authorized by the participant to provide this information. Participants should notify the investigator in writing of the decision to withdraw consent from future follow-up, whenever possible. The withdrawal of consent should be explained in detail in the medical records by the investigator, as to whether the withdrawal is only from further receipt of study intervention or also from study procedures and/or posttreatment study follow-up, and entered on the appropriate CRF page. In the event that vital status (whether the participant is alive or dead) is being measured, publicly available information should be used to determine vital status only as appropriately directed in accordance with local law.

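### The ECG rule in Protocol Section 7.1 orders withdrawal from the study where the rest of the section orders a drug stop with follow-up (minor)

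*Protocol*

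**What the plan says.** Section 7.1 of the protocol sets out when study drug is stopped. Its general text says that "discontinuation of study intervention does not represent withdrawal from the study unless the patient requests withdrawal from the study". If drug is stopped for good, "the participant will remain in the study to be evaluated for the End of Treatment visit", which is due within 2 weeks, and "the site staff will follow-up on the participant's vital status at Month 12 from baseline". The stated exception to the Month 12 check is a participant who withdraws consent for any further contact.

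Under ECG Changes, in the same section, there are two criteria: QTcF above 500 msec, and a change from baseline in QTc above 60 msec. The stated consequence is: "A participant who meets either bulleted criterion based on electrocardiogram (ECG) readings will be withdrawn from the study". The next paragraph leaves it to the investigator to decide whether a participant with a clinically significant finding, QTcF changes included, can stay in the study. The text then closes by sending the site to the Schedule of Activities (SoA) "for data to be collected at the time of intervention discontinuation and follow-up".

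Section 7.2 says that a participant who leaves the study is permanently discontinued from both product and study at that time. It adds that uncompleted withdrawal procedures are not protocol deviations as long as safety was preserved.

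**The concern.** An ECG value is not a patient request, so the mandatory ECG sentence does not fit the general rule of its own section. Nor does it fit its own closing reference, which speaks of stopping the intervention. Three different instructions sit under one heading: compulsory study withdrawal, investigator discretion, and follow-up after a drug stop.

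The wording matters because study withdrawal leads the reader to Section 7.2. That section ends participation immediately, prescribes no exit visit, and does not count missed withdrawal procedures as deviations. The participants concerned are those with a QTc signal, in a study whose primary objective is safety. The data at stake are the End of Treatment visit, with its ECG, and the Month 12 vital-status contact.

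**Working it through.** The plan gives no figure on this point. The check is a comparison of texts, followed by date arithmetic on what could be lost.

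**1. Texts side by side**

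| Place in protocol | Trigger | Consequence |
|---|---|---|
| 7.1, general text | Drug definitively stopped | Stays in study; End of Treatment visit; Month 12 vital status |
| 7.1, ECG Changes, rule | QTcF >500 msec or QTc change >60 msec | Withdrawn from study (mandatory) |
| 7.1, ECG Changes, next paragraph | Clinically significant finding, including QTcF change | Investigator decides on continuation |
| 7.1, ECG Changes, closing line | Drug stopped | Data and follow-up per SoA |
| 7.2 | Leaves the study | Off product and off study at once |

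Row 2 cannot be squared with row 1 as worded, and it overlaps with row 3. Section 7.2 does not name an ECG criterion among its reasons for leaving the study, although that list is not worded as exhaustive.

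**2. Scheduled ECGs at risk**

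The SoA marks the 12-lead ECG at Screening, Day 1, Month 1, Month 6 and Month 12/End of Treatment, and not at post-treatment follow-up. That gives 3 post-baseline ECG visits. A trigger at Month 1 or Month 6 leaves one scheduled ECG, at the End of Treatment visit. A Month 12 trigger puts nothing at risk, because Month 12 and End of Treatment share one column.

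**3. Gap to the vital-status contact**

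Target days (SAP Appendix 1.1) are 31 for Month 1, 181 for Month 6 and 361 for Month 12.

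- Month 1 trigger: 361 − 31 = 330 days
- Month 6 trigger: 361 − 181 = 180 days

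**4. Effect on the SAP by-visit summaries**

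Assume that the trigger occurs at a scheduled ECG visit and that drug stops there. The latest End of Treatment visit is target day + visit window + 14 days.

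- Month 1 trigger: 31 + 7 + 14 = Day 52. This lies in the Month 1 window (Days 16 to 105), which already holds the triggering visit. For endpoints assessed only at Months 6 and 12, Day 52 is before Day 91 and enters no window.
- Month 6 trigger: 181 + 14 + 14 = Day 209. This lies in the Month 6 window (Days 106 to 270, or 91 to 270), which also already holds a value.

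No cell is emptied, but the reported value can change, because the SAP takes the observation closest to the target day. With a Month 1 visit on Day 31 − 7 = 24, an End of Treatment visit on Day 31 would replace it.

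**5. What does not change**

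The safety set needs one dose (SAP Section 4). The TEAE window runs to 28 days after the last dose (SAP Section 3.1). After treatment has begun, adverse event collection ends early only if consent for further information is withdrawn (protocol Section 8.3.1).

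**The case against.** The strongest reply is that the combined text already keeps both duties alive. Anyone withdrawn for QTc has also stopped drug, and the Section 7.1 duties depend on stopping drug. The ECG text itself ends by pointing to the SoA for data after a drug stop. The amendment summary, taken only as evidence of intent, says that the former early-discontinuation visit was removed from Section 7.2 because its requirement had moved to Section 7.1. This stands as far as intent goes: the sentence looks like a drafting slip. It does not remove the conflict, because the operative sentence is mandatory and says something else.

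Four stronger readings are tempting, and the documents do not support them.

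- *The primary endpoint loses data.* A reader might infer that TEAE collection stops at withdrawal. Section 8.3.1 does not say so.
- *An off-drug ECG is lost.* The End of Treatment visit may fall at or just after the last dose, so a washed-out recording is not assured. Section 8.2.3 (continuous monitoring and cardiology consultation for persistent prolongation), unplanned visits, and adverse event follow-up to resolution or stabilisation also protect these participants. They do not replace a scheduled ECG.
- *A mortality analysis is biased.* The SAP has no vital-status or mortality endpoint. Deaths up to 28 days after the last dose are captured as adverse events.
- *The site's termination option must be rewritten too.* Section 7.1 also says "The site has the option to discontinue dosing for this participant and to terminate the participant's study participation", and Sections 6.1 and 6.1.1 carry similar text. That option is discretionary and concerns tolerability or other reasons for stopping. It is a separate matter and need not be settled here.

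Section 7.2.1 shows the protocol's general approach: "Participants who request to discontinue receipt of study treatment will remain in the study and must continue to be followed for protocol-specified follow-up procedures", and "The only exception to this is when a participant specifically withdraws consent for any further contact". It governs participants who ask to stop, not stops required by an ECG, so it is supporting context rather than a second contradiction.

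**Conclusion.** The inconsistency is real and the wording should be corrected; its severity is minor. Read literally, the ECG sentence lets a site omit one End of Treatment visit, which holds the only remaining scheduled 12-lead ECG after a Month 1 or Month 6 trigger. It also lets a site omit one vital-status contact, due 330 or 180 days later at target days. How many participants this would touch cannot be estimated, because the documents give no expected rate of QTc exceedance.

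The safety set, TEAE window and adverse event collection are unchanged, and the SAP summaries are essentially so. The last statement rests on the trigger occurring at a scheduled ECG visit with drug stopped there. A trigger at an unplanned visit between scheduled ones could place the End of Treatment visit in an otherwise empty window.

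**What to change.** Make two edits under ECG Changes in Section 7.1:

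1. Replace the order to withdraw the participant from the study with: *will be discontinued from study intervention and followed per Section 7.1 (End of Treatment visit, post-treatment follow-up and Month 12 vital status) unless consent for further contact is withdrawn*.
2. Add to the following paragraph that the investigator's decision on continuation applies to ECG findings that do not meet the two criteria.

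Sections 6.1 and 6.1.1 need no change for this purpose. The cost is one phrase and one short sentence in the next amendment. No visit, procedure or data item is added, because everything named is already in the SoA or Section 7.1. The investigator keeps discretion for lesser ECG findings.

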### 1.3. Schedule of Activities (SoA)

The SoA table provides an overview of the protocol visits and procedures. Refer to the **STUDY ASSESSMENTS AND PROCEDURES** section of the protocol for detailed information on each procedure and assessment required for compliance with the protocol.

The investigator may schedule visits (unplanned visits) in addition to those listed in the SoA table, in order to conduct evaluations or assessments required to protect the well-being of the participant.

Procedure/ Assessment	Screening	Baseline visit	Month a					
			1 (±1 week)	3 (Tel eph one visit ±2 weeks)	6 (±2 week s)	9 (Tel eph one visit ±2 weeks)	12 (±2 weeks) (or within 2 weeks after End of Treatment)	Post- treatment follow-up (28+7 days after last dose)
	Day-45 to Day 0	Day 1						
Informed Consent	X							
Medical History	X							
Review entrance criteria	X	X						
Full physical examination	X							
Brief physical examination		X	X		X		X	
Height	X							
Weight	X	X	X		X		X	
12 Lead ECG	X	X	X		X		X	
Vital signs b	X	X	X		X		X	
Echocardiogram	X				X		X	
Tissue biopsy or radionuclide bone scintigraphy (99mTc-PYP) c	X							
Laboratory samples								
Hematology	X		X		X		X	
Serum Chemistry	X		X		X		X	
Coagulation (INR, PT, APTT, FIB)	X		X		X		X	
Thyroid-stimulating hormone, total Thyroxine 4 and free Thyroxine 4		X	X		X		X	
Retinol Binding Protein		X			X		X	
Contraception check d	X			X	X	X	X	X
Pregnancy test (only for WOCBP) e	X				X		X	
Serology (HBsAg, anti- HCV, anti-TP and anti-HIV)	X							
Serum/urine test for primary amyloidosis (AL)	X							

Procedure/ Assessment	Screening	Baseline visit	Month a					
			1 (±1 wee k)	3 (Tel eph one visit ±2 wee ks)	6 (±2 week s)	9 (Tel eph one visit ±2 wee ks)	12 (±2 weeks (or within 2 weeks after End of Treatment)	Post- treatment follow-up (28+7 days after last dose)
	Day-45 to Day 0	Day 1						
Mass spectrometry/ Immunohistochemistry f	X							
Genotyping g	X							
Urinalysis	X		X		X		X	
NT – proBNP, Troponin I		X			X		X	
6-MWT		X			X		X	
TTR stabilization, TTR concentration h		X	X		X		X	
Tafamidis concentrations i			X		X		X	
KCCQ j		X			X		X	
EQ-5D-5L k		X			X		X	
SF-12 k		X			X		X	
NYHA classification	X	X			X		X	
Concomitant treatments	X	X	X	X	X	X	X	
Serious and nonserious adverse event monitoring	X	X	X	X	X	X	X	X
Hospitalization determination		X	X	X	X	X	X	

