**Medical Conditions:**

1. Other acute or chronic medical or psychiatric condition including recent (within the past year) or active suicidal ideation or behavior or laboratory abnormality that may increase the risk associated with study participation or study intervention administration or may interfere with the interpretation of study results and, in the judgment of the investigator, would make the participant inappropriate for entry into this study.

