#### **6.1.1. Administration**

Participants will swallow the investigational product whole, and will not manipulate or chew the investigational product prior to swallowing and taking the capsules with a glass of water. Participants will be instructed to dose at a consistent time of day. Participants will be instructed to start taking their medication each day in the morning (AM dosing); however, it is permitted for participants to take his/her medication in the afternoon or evening prior to a clinic visit (eg, the Month 6 visit) when the timing of PK sample collection is prohibitive for adherence with AM dosing. Participants should not take an extra dose of medication in the event that a dose from a previous day is missed and should resume dosing capsules per day from an individual row on the study medication at the next planned dosing time. Similarly, if multiple doses are missed in succession, the participant should resume dosing at the next planned dosing time without taking additional doses to make up for those doses that were missed. Instructions on dosing are provided on the Participant Daily Dosing Diary.

At the end of each visit, sites will instruct participants, in writing on the front of the Participant Daily Dosing Diary, when to take their medication prior to their next study visit. This is especially important if the next visit has a collection of blood sample(s) for PK analysis.

Knowing the actual time of dosing is essential for appropriate analysis of samples for TTR stabilization, TTR concentration, and for tafamidis pharmacokinetic measurements. On the day of the study visit, participants will write the actual time that they took their medication in the Participant Daily Dosing Diary and the site staff will record this dosing time in the case report form (CRF).

On Day 1 (Baseline Visit), participants will be instructed to take their first daily dose of 61 mg tafamidis, after the completion of the baseline procedures and to continue dosing capsules each day in the morning (AM dosing) until the next study visit of Month 1 visit. At the end of the clinic visit, the participants will be reminded to take their medication in the clinic, rather than at home, on the day of the next visit of Month 1, as indicated on the Participant Daily Dosing Diary.

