### 8.2.3. Electrocardiograms

12-Lead ECGs should be collected at times specified in the [SoA](#) using an ECG machine that automatically calculates the heart rate and measures PR interval (PR), QT interval (QT), and corrected QT (QTc) intervals and QRS complex (QRS). All scheduled ECGs should be performed before blood pressure or pulse measurements or blood collection. For ECG recordings, the participants will remain supine for about 5 minutes before recording the ECG.

If a postdose QTcF interval remains  $\geq 60$  msec from the baseline and is  $> 450$  msec; or b) an absolute QTcF value is  $\geq 500$  msec for any scheduled ECG for greater than 4 hours (or sooner, at the discretion of the investigator), or QTc intervals get progressively longer, the participant should undergo continuous ECG monitoring. A cardiologist should be consulted if QTc intervals do not return to less than the criterion listed above after 8 hours of monitoring (or sooner, at the discretion of the investigator).

ECG data will be submitted to a site laboratory for measurement. The final ECG report from the central laboratory should be maintained in the participant's source documentation and be the final interpretation of the ECG recording. Any clinically significant changes from the

baseline/Day 1 ECG may potentially be AEs ([Appendix 7](#)) and should be evaluated further, as clinically warranted.

In some cases, it may be appropriate to repeat abnormal ECGs to rule out improper lead placement as contributing to the ECG abnormality. It is important that leads be placed in the same positions each time in order to achieve precise ECG recordings. If a machine-read QTc value is prolonged, as defined above, repeat measurements may not be necessary if a qualified medical provider's interpretation determines that the QTcF values are in the acceptable range.

ECG values of potential clinical concern are listed in [Appendix 7](#).

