### **6.3.2. Electrocardiograms**

Centrally over-read ECG variables will be summarized by mean change from baseline to each measurement time for heart rate, PR interval, QRS interval, QT interval and QTcF (Fridericia correction) intervals. Additionally, the incidence of categorical increases in QTc intervals will be provided. Categories for QTcF are  $\geq 450$  msec,  $\geq 480$  msec, and  $\geq 500$  msec. Categories for QTcF as change from baseline are  $\geq 30$  msec increase,  $\geq 60$  msec increase and  $\geq 75$  msec increase. QTcF is considered the primary QTc value as this correction is more appropriate. In addition, the number (%) of subjects with normal, abnormal not clinically significant, abnormal clinically significant and unevaluable will also be summarized at each visit.

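### SAP 6.3.2 counts absolute QTcF values (≥450, ≥480, ≥500 msec) as increases without separating those already present at baseline

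*Protocol*

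**What the plan says.** **Reporting.** SAP 6.3.2 states: "Additionally, the incidence of categorical increases in QTc intervals will be provided". Two sets of rows follow. The first is absolute QTcF: ≥450, ≥480 and ≥500 msec. The second is change from baseline: ≥30, ≥60 and ≥75 msec. Protocol 9.4.1.2 has the same sentence and the same rows except ≥75 msec, which SAP 2.1 explains as an addition. SAP 6.3.2 also gives mean changes in each ECG variable and per-visit counts of normal and abnormal tracings. SAP 5.2.1 adds baseline and change summaries with quartiles and extremes. SAP 6.3.2 specifies neither a baseline-by-post-baseline table nor an individual ECG listing.

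**Stopping and entry.** Under ECG Changes, Protocol 7.1 says: "A participant who meets either bulleted criterion based on electrocardiogram (ECG) readings will be withdrawn from the study". One criterion is QTcF above 500 msec, with no reference to baseline; the other is a QTc change above 60 msec. The next paragraph says that after a clinically significant finding "the investigator or qualified designee will determine if the participant can continue in the study". Protocol 5.1 and 5.2 contain no ECG limit. The nearest provision is exclusion 1, which covers conditions that "in the judgment of the investigator, would make the participant inappropriate for entry into this study".

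**The concern.** An absolute value at or above a cut-off is not an increase unless the participant was below that cut-off before treatment. The SAP places both kinds of row under one sentence about increases and never restricts or splits the absolute rows by baseline. With no control arm, nothing in the study shows how many participants would have had these values anyway. Safety is the primary objective, so a reader of the report is likely to use these rows to judge whether the drug prolongs QTcF.

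The plan recognizes the distinction elsewhere. Protocol Appendix 7 limits its 480 msec adverse-event threshold to new prolongation. SAP 6.3.3 compares echocardiograms with baseline, and SAP 6.4 uses a shift table for NYHA class.

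A related, smaller matter is that the 500 msec withdrawal rule in Protocol 7.1 has no numeric counterpart at entry. A candidate above 500 msec before dosing is kept out only by investigator judgment.

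**Working it through.** **Plan's own figure.** The requirement is an 80% probability of at least one event at 3% incidence. 1 − 0.97^53 = 0.801, and ln 0.2 / ln 0.97 = 52.84, rounded up to 53. The figure reproduces. It is not in dispute and serves below only as a denominator.

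**Step 1: two participants the table cannot tell apart.**

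| Baseline → Month 1 (msec) | Change | ≥450 / ≥480 / ≥500 | ≥30 / ≥60 / ≥75 |
|---|---|---|---|
| 480 → 505 (new crossing of 500) | +25 | 1 / 1 / 1 | 0 / 0 / 0 |
| 505 → 505 (pre-existing) | 0 | 1 / 1 / 1 | 0 / 0 / 0 |

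Both meet the first ECG criterion of Protocol 7.1 (505 > 500), and neither meets the second (25 and 0 do not exceed 60).

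**Step 2: the general case.** A post-dose value in the row ≥T that is not in the ≥30 msec row has a baseline above T − 30: above 470 for T = 500, above 450 for T = 480, and above 420 for T = 450. A baseline between T − 30 and T is a new crossing; a baseline at or above T is pre-existing. Both produce the same row counts.

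**Step 3: do the other planned summaries resolve it?**
- Baseline maximum (SAP 5.2.1): if it lies below T, every count in row T is new. If it reaches T, the count cannot be divided.
- Mean change: a group average that does not identify who crossed.
- Normal/abnormal counts per visit: marginal counts, not tied to a QTcF cut-off or to the same participant's baseline.
- Change rows: separate counts, not cross-classified with the absolute rows.

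**Step 4: size per participant.** With 53 treated and a value at the visit from each, the contribution of pre-existing values to a row is 0/53 = 0%, 1/53 = 1.9%, 2/53 = 3.8%, 5/53 = 9.4% or 10/53 = 18.9%. These counts are an assumed range. SAP 6.5 repeats the safety analyses by NYHA class. If the one-third cap in Protocol 4.1 is applied to the 53 treated, class III+ holds at most floor(53/3) = 17, so one value adds at least 1/17 = 5.9 points there.

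**Step 5: illustration with no drug effect.** The documents give no QTcF distribution. Assumptions: normal values, between-patient SD 30 msec, within-patient SD 12 msec, one baseline ECG, and the largest of three post-baseline ECGs.

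| Assumed mean QTcF (msec) | ≥450: any / already at baseline | ≥480: any / already at baseline | ≥500: any / already at baseline |
|---|---|---|---|
| 430 | 38% / 24% | 10% / 5% | 3% / 1% |
| 450 | 63% / 47% | 26% / 15% | 10% / 5% |
| 470 | 83% / 71% | 50% / 35% | 26% / 15% |

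Under these assumptions the rows fill without any effect of the drug, and a large share of each count was present at baseline. The remainder are chance crossings, so a split removes part of the ambiguity, not all of it.

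**Step 6: secondary point.** If a proportion q of otherwise eligible patients exceeded 500 msec before dosing and none were kept out, the chance of at least one among 53 is 1 − (1 − q)^53: 41% for q = 1%, 66% for 2%, 80% for 3%, 93% for 5%. These q values are assumptions; the true one may be zero.

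**The case against.** **On the reporting.** The SAP does compare ECGs with baseline, through mean changes and three change rows. It labels the absolute rows separately from the change rows, so a careful reader need not confuse them. If the baseline maximum is below a cut-off, all counts in that row are new. New clinically relevant findings also reach the adverse-event listing through Protocol 7.1 and Appendix 7. All of this is true and it narrows the point. It does not remove it: none of these outputs divides a row once any baseline value reaches the cut-off, and the adverse-event route depends on investigator judgment.

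**On entry and stop.** A reader might infer that the plan will expose participants to drug and then withdraw them for a finding known beforehand, and that a 500 msec exclusion is therefore required. The documents do not support that.
- ECGs are scheduled at Screening and Day 1, and the Schedule of Activities repeats "Review entrance criteria" at both.
- On Day 1 participants "take their first daily dose of 61 mg tafamidis, after the completion of the baseline procedures", so the tracing is available in time for exclusion 1 to be used.
- The ECG rule is not limited to post-dose tracings and could be read to remove such a person before dosing. The opening of 7.1, "Participants with one or more of the following criteria in the study duration will discontinue the investigational drug", favors an on-treatment reading but does not settle it.
- An exclusion above 500 msec would leave a candidate at 495 msec eligible, with a 6 msec drift enough to trigger the stop.
- A stop conditional on baseline is an alternative to excluding patients with a rare disease, and the choice is debatable.

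What stands is that entry above 500 msec rests on judgment while the stop is numeric. The wording of 7.1 is also in tension with itself, since withdrawal is mandatory in one sentence and continuation is left to the investigator in the next paragraph.

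**Conclusion.** The reporting point holds and is minor. As specified, the absolute QTcF rows cannot separate pre-existing from newly occurring values, and a single-arm study has no other means of doing so. Each pre-existing value is worth 1.9 points overall with 53 treated, and at least 5.9 points in NYHA III+ under the cap. The total effect is unknown and may be zero, because the documents give no baseline QTcF; the percentages in Steps 5 and 6 rest wholly on stated assumptions.

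A reader might also infer that the primary safety result or the sample size is compromised. Neither is. The primary endpoint is the incidence of treatment-emergent adverse events, anyone who takes one dose stays in the safety population, and 53 reproduces. Nor do the documents show that the 500 msec stop is wrong. Protocol 8.2.3 also uses an absolute threshold there, although it leads to monitoring and not to withdrawal.

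The entry-versus-stop mismatch is secondary and optional.

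**What to change.** **SAP 6.3.2 (main change).** For each absolute category (≥450, ≥480, ≥500 msec), report participants already at or above the cut-off at baseline separately from those newly reaching it after dosing, with those below the cut-off at baseline as the denominator for the latter. A baseline-by-post-baseline shift table would do equally well. Show missing baselines as their own category, as SAP 6.3.3 does for echocardiography. List the baseline QTcF of any participant withdrawn on a QTcF criterion. The cost is three split rows and a short listing, all from ECGs already scheduled; no new data are needed.

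**Protocol (optional, only if enrollment is still open).** Align entry with the stop in 7.1, either by a numeric pre-dose QTcF limit confirmed on a repeat ECG or by stating how the stop applies to a participant already above 500 msec. This is a clinical decision for the sponsor. The first route costs one exclusion line, a repeat ECG for the few candidates above the limit and possibly some eligible rare-disease patients. The second makes a safety stop conditional on baseline. If enrollment has closed, only the SAP change still applies.
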